Full study protocol and statistical analysis plan

Official Title of the study:

Cognitive progressive muscular relaxation therapy on couples undergoing IVF-ET

Date of the document:

20th April 2019

Contents:

- 1. Participant Flow
- 2. Baseline Characteristics
- 3. Outcome Measures
- 4. Adverse Event Information
- 5. Limitations and Caveats
- 6. Certain Agreements
- 7. Results Point of Contact

1. Participant Flow

Recruitment Details

We will choose Infertility Reproductive Center, Second Xiangya Hospital, Central South University to recruit the participants. The recruitment will start at May 1st 2019. The recruitment announcement will be distributed to the participants via notice board in the department.

Pre-assignment Details [*]

We firstly will assess the recruited people to ensure meeting the inclusion and exclusion criteria. Then the final enrolled participants can be sure and randomized assignment will be conducted.

Enrollment (total, anticipatory)	138			Record the number of the eligible and the excluded
Allocation (randomized)	Group A	Group B	Group C	Record the number of the received and the unreceived
	46	46	46	
Follow-up (immediately after intervention)				Record the number of the received and the unreceived

Arm/Group Information *

There are three groups in the study.

Arm/Group Title *

Women intervention group= Group A

Couple intervention group= Group B

Controlled group= Group C

Arm/Group Description *§

Women intervention group: Only women will be intervened by Cognitive progressive muscular relaxation therapy.

Couple intervention group: Both couple will be intervened by Cognitive progressive muscular relaxation therapy.

Controlled routine activity group will have routine nursing care delivered by nurses.

Period(s) *

There is only one stage in the study.

Period Title *

Overall Study.

Started *

There will be 138 participants initiating the intervention.

Those 138 participants will be randomly assigned to three groups with around 46 participants in each group.

Completed *

We will do follow-up, and the number in the follow-up will be recorded.

Milestone Title [*]

Before the intervention, we will measure the participants, and the stage is defined as T0.

We will do follow-up immediately after intervention, defined as T1.

Reason Not Completed Type [*]

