- Anxiety: Anxiety in recent two weeks measured by Zung Self-rated Depression Scale (SAS). It is a self-reported scale by adding up 20 items and the total score ranges from 20-80, with higher score reflects higher anxiety.
- Sleeping quality: a reflection of one's mood in recent month measured by Pittsburgh sleep quality index(PSQI). It is a self-reported scale, with total score higher than 19 reflects sleeping disorder. The differences within each time frames are the changes of sleeping quality
- Concentration of dehydroepiandrosterone in blood: a kind of hormone that reflects the

person's psychological stress.

- Success of IVF-ET: we will follow up the success of the participants of each group.

Outcome Measure unit *

The depression, anxiety, and sleeping quality are measured by scales with no unit.

Dehydroepiandrosterone has its concentration unit of pg/ml.

Outcome Measure Time Frame *

There will be two measurements, before the intervention and immediately after intervention.

They are defined as T0, T1.

Analysis Population Information

Overall Number of Participants Analyzed *

There will be 150 participants totally enrolled in the study.

Outcome Measure Data Table

Measure Type *

- Mean

Measure of Dispersion/Precision *

- Standard Deviation

Outcome Data *

The measurement value(s) for each outcome measure cannot obtain right now since the study has not been started.

Statistical Analysis Overview

Comparison Group Selection [*]

We will compare three groups' data.

Type of Statistical Test [*]

- Superiority
- Other (descriptive analysis)

P-Value [*]

P-Value will be set at 0.05.

Method [*]

- ANOVA
- Chi-Squared
- t-Test, 2-Sided
- Other: repeated measurement of variance analysis within different measurements among different groups

Estimation Parameter [*]

- Mean Difference (Final Values)

4. Adverse Event Information

Time Frame *§

The intervention lasts around 30 days, with 6 times, and we will record the adverse event at each time.

Adverse Event Reporting Description [*]

We will add relevant information about adverse event after finishing the study.

Collection Approach for Table Default *§

- Systematic Assessment: The psychotherapist will routinely determine whether or not certain adverse events have occurred through regular investigator assessment during intervention and in each follow-up.
- Non-Systematic Assessment: Self-reporting by participants or occasional assessment by the psychotherapist.

Adverse Event Term *

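### The only estimate named is a final-value difference that uses no T0 data; the competing tests are unranked and no T0-adjusted analysis is specified

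*Combined protocol and SAP*

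**What the plan says.** Section 3, Outcome Measure Time Frame, sets the schedule: "There will be two measurements, before the intervention and immediately after intervention". Section 1, Milestone Title, labels the first of these: "Before the intervention, we will measure the participants, and the stage is defined as T0". The three scales (SDS, SAS, PSQI) and DHEA all fall under that time frame.

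The Statistical Analysis Overview in Section 3 gives one estimation parameter, "Mean Difference (Final Values", and ties it to no particular outcome. Its Method list contains ANOVA, chi-squared, a two-sided t-test and "repeated measurement of variance analysis within different measurements among different groups". The list does not say which method governs, which outcome or contrast each serves, or which repeated-measures effect is to be tested.

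The PSQI entry under Outcome Measure Title adds "The differences within each time frames are the changes of sleeping quality", which points to change rather than to the final value. Section 2 compares the groups at baseline by ANOVA and chi-squared, but it does not carry any T0 value into the outcome analysis.

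On size, Section 1 says "Those 138 participants will be randomly assigned to three groups with around 46 participants in each group". Section 3 says "There will be 150 participants totally enrolled in the study".

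**The concern.** With one pre- and one post-treatment measurement, the listed methods can answer at least three different questions:

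- a comparison of T1 values alone;
- a comparison of changes, which is what the group-by-time interaction amounts to with two time points;
- a comparison of the average of T0 and T1, which is the repeated-measures group main effect.

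They differ in power and can give different verdicts on the same data. For PSQI the text points both to change and to final values.

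The analysis that would normally be preferred here, T1 compared between groups with T0 as a covariate, is absent, although its data are already collected. Three things are at stake: precision, protection against a chance T0 imbalance in the allocation actually obtained, and a commitment to one analysis before the results are known. Bias is not at stake, because a final-value comparison is unbiased over randomisation.

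**Working it through.** **What can be reproduced.** The documents give no effect size, SD, T0–T1 correlation or power, so the sample size cannot be derived from a power formula. Only 3 × 46 = 138 can be checked, and it is correct. Everything below is therefore an illustration.

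**Inputs.** From Section 1: 46 per arm. From Section 3: significance level 0.05, two-sided t-test. Assumed: independent participants, one pairwise comparison, a T1 effect of d = 0.5 SD, a T0–T1 correlation ρ of 0.2 to 0.7, and equal SDs at T0 and T1 unless stated.

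**Variance of each contrast, with T1 variance set to 1.**

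- Final values: 1
- Change (group-by-time): 2(1 − ρ)
- ANCOVA on T0: 1 − ρ²
- Repeated-measures group main effect: effect d/2, variance (1 + ρ)/2

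For relative variance v, the noncentrality is effect ÷ √(2v/46), on 90 degrees of freedom (89 for ANCOVA). For final values it is 0.5 ÷ √(2/46) = 0.5 ÷ 0.209 = 2.40, which gives power 0.660. For ANCOVA at ρ = 0.5 it is 2.40 ÷ √0.75 = 2.77, which gives 0.782.

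| ρ | Final | Change | Group main effect | ANCOVA | 46/(1 − ρ²) |
|---|---|---|---|---|---|
| 0.2 | 0.660 | 0.466 | 0.334 | 0.678 | 47.9 |
| 0.3 | 0.660 | 0.518 | 0.313 | 0.701 | 50.5 |
| 0.4 | 0.660 | 0.581 | 0.294 | 0.735 | 54.8 |
| 0.5 | 0.660 | 0.660 | 0.278 | 0.782 | 61.3 |
| 0.6 | 0.660 | 0.756 | 0.264 | 0.843 | 71.9 |
| 0.7 | 0.660 | 0.865 | 0.251 | 0.913 | 90.2 |

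The last column is the number per arm that a final-value analysis would need to match the precision of ANCOVA with 46.

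**Unequal SDs.** If the T0 SD is k times the T1 SD, the change variance is 1 + k² − 2ρk. For k from 0.8 to 1.25, change-score power runs from 38% to 91%. Final-value and ANCOVA power do not change.

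**Larger arms.** With 150 participants (50 per arm), power is 70% for final values and 71%–93% for ANCOVA.

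**Disagreement between the final-value and change tests (simulation, equal SDs).** One test is significant and the other is not in about:

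- 7%–9% of trials with no effect
- 15%–25% at 0.2 SD
- 30%–32% at 0.5 SD
- 3%–14% at 0.8 SD

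With k from 0.8 to 1.25, the range at 0.5 SD is 24%–40%.

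**Type I error if either test may count.** It is about 8%–10% for one outcome and one contrast. Three-arm omnibus F tests give a similar 8.6%–9.6%.

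**Chance imbalance.** A T0 difference of 0.3 SD between two arms is expected to shift the final-value difference by ρ × 0.3. That is 0.15 SD at ρ = 0.5 and 0.21 SD at ρ = 0.7, against a standard error of √(2/46) = 0.209 SD. ANCOVA removes this shift.

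**The case against.** The strongest reply is that the named parameter is a quantity, not an estimator. ANCOVA estimates the same T1 difference, so the label does not forbid adjustment. Repeated-measures ANOVA is also listed and does use T0, and its most natural target is the group-by-time interaction rather than the group main effect. This is correct as far as it goes. T0 is unused by the named estimate, not by every listed method, and the main-effect column shows only what one permitted reading would cost. But the plan does not name the interaction, the interaction does not produce the final-value estimate, and nowhere is adjustment mentioned.

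An omnibus ANOVA followed by pairwise t-tests on T1 could also be complementary steps rather than rivals. That is fair, and it leaves the central ambiguity as final value against change. The PSQI sentence is loosely worded and is weak evidence alone, but it does point to change.

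The T0 measurement of DHEA follows from the general time frame rather than from a sentence about DHEA itself.

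Finally, every power figure rests on assumed inputs. At ρ of 0.2 to 0.3 the ANCOVA gain is small: 68%–70% against 66%, worth about 2 to 5 participants per arm. The type I error figure applies only if either result is allowed to count, which the plan neither says nor rules out. These points limit the size of the problem but do not remove it.

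**Conclusion.** The concern holds. The plan names one estimate that uses no T0 data, lists tests that answer different questions without saying which governs, and specifies no T0-adjusted comparison.

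Under the stated assumptions, ANCOVA is at least as powerful as final values or change scores at every correlation and SD ratio examined. Its advantage over final values grows from about 2 percentage points at ρ = 0.2 to about 25 at ρ = 0.7. The selection problem does not depend on a high correlation: at 0.5 SD the two main candidates disagree in roughly a quarter or more of trials throughout.

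The trial is not invalid as written. This is a change that should be made, and confidence in the point is high because it rests on what the text states and omits; only its size depends on assumed values.

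**What to change.** In Section 3, Statistical Analysis Overview, state that the governing analysis for SDS, SAS, PSQI and DHEA is an ANCOVA of the T1 value on group and the same measure's T0 value. Replace the final-value parameter with the T0-adjusted mean difference and its 95% confidence interval. Label the repeated-measures ANOVA as supportive, naming the group-by-time interaction as the effect tested, and state that the unadjusted ANOVA and t-test do not govern the conclusion. Reword the PSQI entry to match, and confirm that DHEA is drawn at T0. If both partners' data are analysed, the model must also allow for couples. IVF-ET success has no T0 value and lies outside this change.

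The cost is wording only, with no added participants, visits or measurements. A couple identifier is needed in the data if both partners are analysed.

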We will record the exact reason (Adverse Event) why participants do not complete the study. The reason may be death, lack of efficacy, lost to follow-up, illness, withdrawal by subject or others.

2. Baseline Characteristics

Arm/Group Information *

Chi-square test will be applied to figure out the difference of enumeration data among three groups. ANOVA will be applied to test the difference of measurement data among three groups. F values and χ^2 values will be displayed to show the baseline data are no different in three groups.

Arm/Group Title *

Women intervention group= Group A

Couple intervention group= Group B

Controlled group= Group C

Arm/Group Description *§

All the recruited participants will be numbered and randomly allocated into three groups by random number table. The grouping results will be announced to the participants according to the random number table.

Overall Number of Baseline Participants *

There will be 138 participants initiating the intervention.

Baseline Measure Information *

A group of demographic characteristics will be measured in the study, including gender, age, marital status, income per month, etc.

Baseline Measure Title *

- Age * : Continuous(years)
- Gender * : Female, Male
- Years after diagnosed with infertility: Continuous(years)
- Income per month: Categorical:
 - <=1000 RMB
 - >1000 and <2000 RMB
 - >=2000 RMB
- Educational level: Categorical:
 - Junior high school
 - Senior high school
 - College and above

Measure Type *

- Count of Participants: Gender
- Mean: Age, Years after diagnosed with infertility
- Number: Income per month, Educational level

Measure of Dispersion *

- Standard Deviation
- Inter-Quartile Range
- Full Range

Baseline Measure Data *

The value(s) for each baseline measure, for each group and overall cannot obtain right now since the study has not been started.

3. Outcome Measures

Outcome Measure Information *

A questionnaire will be used during each measurement, including several scales in it.

Dehydroepiandrosterone will also be tested.

Outcome Measure Type *

- Primary and secondary

Outcome Measure Title *

- Depression: depressive mood in recent two weeks measured by Zung Self-rated Depression Scale (SDS). It is a self-reported scale by adding up 20 items and the total score ranges from 20-80, with higher score reflects higher depression.

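### Scheduled adverse event checks follow the six therapy times, and no section gives Group C a scheduled check before T1, so the by-group table of non-serious events may partly reflect how often people were asked

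*Combined protocol and SAP*

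**What the plan says.** All references are to the combined protocol and SAP.

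- **Schedule** (Section 4, Time Frame): "The intervention lasts around 30 days, with 6 times, and we will record the adverse event at each time".
- **Systematic collection** (Section 4, Collection Approach): "The psychotherapist will routinely determine whether or not certain adverse events have occurred through regular investigator assessment during intervention and in each follow-up".
- **Non-systematic collection** (same place): "Self-reporting by participants or occasional assessment by the psychotherapist". This route is not limited to any group.
- **Group C** (Section 1, Arm/Group Description): "Controlled routine activity group will have routine nursing care delivered by nurses". No therapy sessions and no psychotherapist are mentioned for this group.
- **Follow-up** (Section 1, Milestone Title): "We will do follow-up immediately after intervention, defined as T1". Section 3 likewise gives two measurements, T0 and T1. It also promises to follow up IVF-ET success in each group, without a date.
- **Non-completion** (Section 1, Reason Not Completed Type): "We will record the exact reason (Adverse Event) why participants do not complete the study".
- **Reporting** (Section 4, Adverse Event Term): three tables by group, covering all-cause mortality, serious events and other events. Psychological discomfort is named as the most likely event.
- **Wording that points the other way** (Section 1, Started, repeated in Section 2): "There will be 138 participants initiating the intervention". The 138 include Group C.

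**The concern.** Psychological discomfort is subjective and may be brief, so whether it is recorded depends heavily on whether someone asks. If one group is asked at every therapy session and another only at the end, the table of non-serious events can show an excess under therapy when the true rates are equal. The reverse error is as awkward: a real excess of discomfort under therapy could be dismissed as a product of closer questioning. Either way the table could not be interpreted, and equal collection cannot be restored once T1 has passed.

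Deaths and serious events are likely to come to light however often people are asked, so those two tables are not the worry.

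The depression and anxiety scales (past two weeks) and the sleep index (past month) are given to all groups at T0 and T1. They are a partial, even-handed check on lasting distress. They do not feed the adverse event tables and could miss short-lived discomfort at a session.

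**Working it through.** The plan gives no adverse event rate and no calculation based on one, so there is no figure of its own to reproduce. Group sizes agree: 3 × 46 = 138.

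**Step 1. Count the scheduled checks.**

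| | During the ~30 days | At T1 | Total |
|---|---|---|---|
| Treated participants | 6 | 1, or 0 extra if T1 falls at the sixth time | 6 to 7 |
| Group C, natural reading | none stated | 1 | at least 1 |
| Group C, if the six times cover all groups | 6 | as for treated | 6 to 7 |

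The figure for Group C is a minimum. Occasional psychotherapist assessment is open to every group, and the IVF-ET success follow-up, whose timing is not stated, might be a further contact.

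**Step 2. Illustrate the size.** Every rate here is an assumption. Let q be the chance of discomfort on one occasion, the same in every group; k the number of occasions; and r the chance that an earlier occasion is recalled at T1 or self-reported. Each check is taken to find whatever is present. Then the probability of at least one recorded event is

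- treated: 1 − (1 − q)^k
- Group C: 1 − (1 − q)(1 − qr)^(k−1)

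With q = 0.05 and k = 7:

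- treated: 1 − 0.95^7 = 0.302; × 46 = 13.9 people
- Group C, r = 0: 0.050; × 46 = 2.3
- Group C, r = 0.5: 1 − 0.95 × 0.975^6 = 0.184; × 46 = 8.5
- Group C, r = 1: 0.302; × 46 = 13.9

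**Step 3. Vary the inputs.** Expected people with a recorded event, out of 46:

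| q | k | Treated | Group C, r = 0 | r = 0.5 | r = 1 |
|---|---|---|---|---|---|
| 0.02 | 7 | 6.1 | 0.9 | 3.6 | 6.1 |
| 0.05 | 6 | 12.2 | 2.3 | 7.5 | 12.2 |
| 0.05 | 7 | 13.9 | 2.3 | 8.5 | 13.9 |
| 0.10 | 7 | 24.0 | 4.6 | 15.6 | 24.0 |

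**Step 4. Let distress persist within a person.** Independent occasions exaggerate the gain from repeated asking. Let each person's q follow a beta distribution with mean 0.05 and within-person correlation 0.3. Then a + b = 0.7/0.3 = 2.333, a = 0.05 × 2.333 = 0.117 and b = 2.217. The treated probability is 1 − ∏(b + i)/(a + b + i), for i = 0 to k − 1. The Group C probability is the Step 2 formula averaged over that distribution.

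| k | Treated | Group C, r = 0 | r = 0.5 | r = 1 |
|---|---|---|---|---|
| 7 | 0.169 (7.8 people) | 2.3 | 5.7 | 7.8 |
| 6 | 0.157 (7.2 people) | 2.3 | 5.3 | 7.2 |

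With correlation 0.3 and 50% recall, the gap is about two people per group.

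**The case against.** The strongest reply is that this is an ambiguity, not a demonstrated flaw. The recording sentence is not restricted by group, all 138 participants are described as starting the intervention, and the tables are promised for every group. The six times could therefore be calendar points for everyone, and the imbalance would vanish. That reading stays open. But Group C is assigned routine care, so the phrase about 138 people cannot be literally true of it, and no section gives that group a timetable or an assessor.

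Several stronger readings may tempt a reader; the documents do not support them.

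- **Group C goes unchecked, or is checked exactly once.** Systematic assessment covers follow-up, and self-report and occasional assessment are open to all groups. One is a floor, not an established count.
- **The imbalance would yield a false significant result.** The plan names no test for adverse events. Its methods are listed under outcome measures, and Section 4 promises only summary tables.
- **14 against 2 is the expected distortion.** That is the extreme of the 5% illustration: seven independent occasions, with nothing recalled or self-reported. The model also gives Group C the same discomfort as people in therapy, to isolate the effect of asking. The plan's sentence on the cause of discomfort breaks off and cannot confirm this.
- **Group A has the same problem internally.** Section 1 says: "Women intervention group: Only women will be intervened by Cognitive progressive muscular relaxation therapy". If male partners were counted, they would lack therapy times too. But the documents do not say whether the 46 are women, individuals or couples, so no figure for Group A can be supported.

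**Conclusion.** The concern holds in a limited form. On the more natural reading, scheduled checks number 6 or 7 for treated participants and at least one for Group C, and the descriptive non-serious table may then partly measure frequency of asking. The effect is nil if the six times cover all groups or if recall at T1 is complete. Otherwise, with the assumed 5% per occasion, 46 per group and 7 against 1 checks, it runs from no difference, through about 8 against 6, to 14 against 2. The documents give no basis for choosing a point in that range. The point is worth acting on because the remedy is cheap and must be in place before T1; confidence is medium, given the rival reading.

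**What to change.** 1. State whether the six recordings apply to all three groups, and who assesses Group C.
2. Add one fixed, self-completed adverse event question to the T1 questionnaire, covering the time since T0 and worded identically for every participant.
3. Ask the same question when the reason for non-completion is recorded for anyone who leaves before T1.
4. Use that item for the descriptive between-group summary of non-serious events. Report session-prompted and spontaneous events separately by group, so that none are lost. Leave the mortality and serious event tables as planned.

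**Cost.** One question at T1 and the same question at exit. No visits are added and Group C's routine care is unchanged.

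**Downsides.** The item relies on about 30 days' recall and may miss mild events. Participants know their group (Section 2), those already asked at sessions may recall somewhat more, and Section 5 itself cautions about self-report. Leavers who cannot be reached will have no answer, so their number should be shown by group. The exit question matters: if an assumed 10% left before T1 (0.10 × 46 = 4.6 people), a T1-only item would lose about 4.6 × 0.302 = 1.4 of the 13.9 people with discomfort if leaving were unrelated to it, and up to 4.6 if every leaver had it.

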The most possible adverse event may be the psychological discomfort because the participants.

We will provide information for in three tables summarizing adverse events in each group,

including all-cause mortality, serious adverse events, and other (not including serious) adverse events.

Organ System *

- Psychiatric Disorders

5. Limitations and Caveats

The measurements are mostly based on self-reported scales and may lead to unreliable data. We will give instruction before fulfilling the questionnaire to ensure the participants understood.

6. Certain Agreements

Are all PIs Employees of Sponsor? *

- No: The principal investigator is not an employee of the sponsor

There is no agreement between the agent (university) and the principal investigators. The principal investigators are graduate students in the university. The principal investigators (PIs) can discuss the results of the study at a scientific meeting or any other public or private forum, or to publish in a scientific or academic journal information concerning the results of the study.

7. Results Point of Contact

Name or Official Title *

Professor: [name]

Position title: Director of Nursing Psychology Research Center

Organization Name *

Nursing Psychology Research Center, Xiangya School of Nursing, Central South University

Phone: *§

[name]

Email: *§ [contact]

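### Individual worsening on the SDS and SAS is neither counted nor linked to the safety tables, although psychological discomfort is the harm the plan considers most likely

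*Combined protocol and SAP*

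**What the plan says.** **Expected harm.** Section 4, Adverse Event Term: "The most possible adverse event may be the psychological discomfort because the participants". The sentence gives no cause in the text available. Psychiatric Disorders is the only organ system listed.

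**Detection.** Section 4, Collection Approach, sets out two routes. The systematic route is: "The psychotherapist will routinely determine whether or not certain adverse events have occurred through regular investigator assessment during intervention and in each follow-up". The non-systematic route is: "Self-reporting by participants or occasional assessment by the psychotherapist". Neither comes with a definition, scale or threshold. On timing, section 4 says: "The intervention lasts around 30 days, with 6 times, and we will record the adverse event at each time". Section 1 adds that reasons for non-completion, including illness and withdrawal, are recorded.

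**Control arm.** Section 1: "Controlled routine activity group will have routine nursing care delivered by nurses". No psychotherapist sessions are described for Group C.

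**Scores held.** Section 3 specifies two self-completed scales, the SDS for depression and the SAS for anxiety. Each has a total of 20 to 80, higher being worse, and recalls the last two weeks. On timing: "There will be two measurements, before the intervention and immediately after intervention". All three groups are compared.

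**How the scores are used.** The outcome table in section 3 is mean with standard deviation, and the estimate is the mean difference in final values. The methods are ANOVA, t-test, chi-squared and repeated-measures analysis of variance, with descriptive analysis also listed.

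**Safety tables.** Section 4 plans three tables by group: all-cause mortality, serious events and other events. None refers to the SDS or SAS.

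**The concern.** The trial collects, in every group and at the same two times, a direct patient-reported measure of the kind of harm it expects, and uses it only to look for benefit. A mean, or a mean difference in final values, describes the group. It does not say how many people moved the wrong way. Repeated-measures analysis adds time but stays at group level.

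Adverse event recording is a weak substitute for comparing arms on this harm. It has no criteria, and its schedule follows six intervention times that Group C, on the description given, does not have. Ascertainment may therefore differ between the active groups and the control. The report could show improved mean scores and few psychological events while the trial's own data contain an unreported minority who deteriorated.

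**Working it through.** The plan gives no figure to reproduce. It states no effect size, SD, power or deterioration rate. The check is therefore a comparison of the text, followed by illustrations with assumed values.

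**1. Is there a planned count of worsening?** Under the section 3 methods, chi-squared and descriptive analysis could in principle deliver one, but neither is tied to the SDS or SAS and no worsening category is defined. In section 4, no sentence brings a score into a safety table. So there is no planned count.

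**2. Can the count be recovered from the planned table?** It cannot. The SD of change is √(s0² + s1² − 2ρ·s0·s1), where s0 and s1 are the SDs at T0 and T1 and ρ is the within-person correlation. The planned table would not give ρ, and even the SD of change would give a count only under an assumed distribution.

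**3. Can a favourable mean coexist with deterioration?** Take 46 in an active group (section 1). Assume 40 change by −6 points and 6 change by +10:

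- mean change = (40 × −6 + 6 × 10)/46 = −180/46 = −3.9
- share worsening = 6/46 = 13.0%

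For a less contrived version, assume individual change is normal. Then P(worsening by at least t) = 1 − Φ((t − mean change)/SD of change). With t = 5 points, chosen only for illustration:

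| Assumed mean change | SD 6 | SD 8 | SD 10 |
|---|---|---|---|
| −3 | 9.1% (4.2 of 46) | 15.9% (7.3) | 21.2% (9.7) |
| −5 | 4.8% (2.2) | 10.6% (4.9) | 15.9% (7.3) |
| −8 | 1.5% (0.7) | 5.2% (2.4) | 9.7% (4.5) |

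The same mean improvement of 5 points is compatible with about 2 or about 7 people worsening by 5 points or more, depending on the assumed SD.

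**4. Would counting any rise do?** No. With no true change, this model has half of participants rising by chance. Even with t = 5 and no true change, the shares are 20.2%, 26.6% and 30.9% at SD 6, 8 and 10. A threshold is needed, and so is the Group C comparison.

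**5. How precise would the comparison be?** The half-width of a 95% interval for a difference, with equal proportions p and 46 per group, is 1.96 × √(2p(1 − p)/46).

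- p = 0.13: 1.96 × √(0.2262/46) = 0.137, about ±14 percentage points
- p = 0.40: 1.96 × √(0.48/46) = 0.200, about ±20 percentage points

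Power to separate 10% from 20% at two-sided 0.05 is about 27%. The table is for estimation and display, not for testing.

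**6. What would the scores miss?** Two-week recall at T1 reaches back 14 of about 30 days, so roughly the first 16 days fall outside it.

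**The case against.** The case against has real weight. Harm collection is not neglected: one route is labelled systematic, events are recorded at six times, reasons for non-completion are kept, and three tables by group are planned. The SDS and SAS may also be a poor match for the named harm. Discomfort could be brief distress in a session, better caught by recording at each time than by one two-week recall at the end. People who withdraw because they feel worse may have no T1 score. Section 5 itself warns that self-reported scales may be unreliable. Between-group intervals will be wide, and two scales with two active groups give four of them.

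Most of this stands, and it shapes the remedy. It argues for a threshold rather than any rise, for showing missing T1 scores, and for a supplementary table. It does not remove the gap. The plan relies on the same scales to show benefit, noise affects all groups, and the control column shows its size.

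A reader might infer three stronger things that the documents do not support:

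- **That the assessor is the person giving the therapy, and so has a conflict of interest.** The plan says only the psychotherapist and never states who delivers the intervention.
- **That worsening reaches the tables only if the psychotherapist judges it an event.** Participant self-report is a separate route. A worsened score could also be recorded as an event, although nothing requires it.
- **That Group C is not assessed for harm.** Systematic assessment also covers each follow-up. The plan does not give Group C's schedule, so unequal ascertainment is possible but not shown.

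**Conclusion.** The point holds as a gap in safety reporting, not as an error in the efficacy comparison. The plan names its expected harm, gives no criteria for detecting it, and measures closely related symptoms in a way that would compare the groups evenly. It then neither counts individual worsening nor brings it into the safety tables.

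The size cannot be derived from the documents. Under the assumed values above, a group with a mean improvement of 3 to 8 points could contain between 1.5% and 21.2% of participants worsening by 5 points or more, about 1 to 10 of 46. These figures rest on a normal model and assumed SDs, and show only that the planned summaries could not reveal such a share. The argument does not depend on exact group size. Section 3 gives 150 participants against 138 elsewhere, and at 50 per group the ±14 points would be about ±13 (1.96 × √(0.2262/50) = 0.132).

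**What to change.** Add a supplementary safety table, by group, containing:

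- the distribution of individual T0-to-T1 changes in SDS and in SAS;
- the number and percentage worsening by at least a threshold that the sponsor fixes and justifies before data are seen, since the documents offer none;
- 95% confidence intervals for each active group minus Group C;
- the number with missing T1 scores and the reasons, beside the counts.

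Use the same unit of analysis in all groups, either the woman or each partner separately, because both partners are treated in Group B. Keep psychotherapist-recorded events and self-reported events as separate lines, so that the sources are not merged.

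The cost is a little more analysis of data already planned, with no new visit, measurement or staff. The drawbacks should be stated with the table. The intervals will be wide. Some worsening will be noise or related to IVF, which the Group C column helps to gauge. Transient discomfort early in the intervention will not be captured, so adverse event recording must continue alongside.
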